6.2 Sample Size

A formal sample size was not conducted for this study; however, five patients with three sets of images each are required.

7 ADDITIONAL DATA ANALYSES

7.1 Other Endpoints/Measurements

Subject disposition, demographics and physical assessments will be summarized and listed. SAEs related to the procedure will be listed. SAEs will be coded according to MedDRA. In addition, Tc-99m MAA administration, and its deposition in critical organs assessed by SPECT-CT/SPECT will also be listed.

Disposition

- Number of subjects screened

- Number and percentage of subjects in ITT population and PP population
- Number of subjects completing the study
- End of study reason
 - Investigator withdrawal
 - Subject withdrawal
 - Death
 - Other

Demographic

- Age at consent (years)
- Gender (Male, Female, Other),
- Race (American Indian or Alaska Native, Asian, Black or African American, Native Hawaiian or Other Pacific Islander, White, Not reported, Unknown, Other)
- Ethnicity (Hispanic, Latinx, or of Spanish origin, Not Hispanic, Latinx or of Spanish origin, Not reported, Unknown)

Physical Assessments

- Height (m)
- Weight (kg)
- BMI (kg/m^2) (calculated as weight in kg divided by square of height in m)

HCC History

- Time since diagnosis (months). It is calculated as the days between HCC diagnosis for current treatment and the administration of Tc-99m MAA divided by 30.4375.

7.2 Protocol Deviations

The inclusion and exclusion criteria were developed to minimize the number of protocol deviations in this study. Any protocol deviations that are captured will be listed.

8 CHANGES TO PLANNED ANALYSES

Any changes to the planned statistical analyses made prior to performing the primary analyses will be documented in an amended SAP approved prior to performing the analyses. Changes from the planned statistical methods after performing the analyses will be documented in the clinical study report along with a reason for the deviation.

9 VALIDATION

All clinical data reports generated per this plan will be validated through the internal validation process used by the independent CRO. BSC Global WI [90702587](#): Clinical Data Reporting Validation may be used as a guidance. Statistical analyses and validation will be done by the independent CRO.

10 PROGRAMMING CONSIDERATIONS

All statistical programming tasks will be performed by the independent CRO. All programming considerations are aimed at facilitating the programming codes generation (e.g. SAS codes).

In general, data listings should be sorted by subject ID and visit/collection dates.

In adverse events, the sorting sequence should be subject ID and the start date of the event. Other sorting sequence that differs from these will be specified. Table and listing display should follow the guidelines listed below:

- All data in the listings should represent the original values that were recorded in the eCRFs, unless otherwise specified.
- Missing values should be printed as blanks in the listings.
- Dates should be printed in Date9 format (DDMMYY YYYY).
- In general, for categorical variable summary, if there is missing data, an additional category of ‘Missing’ should be created, and the number and percentage should be provided.
- In general,
 - the mean (standard deviation) of a set of values should be printed out to one (two) more decimals than the raw value.
 - the median and percentiles should be printed out to one more decimals than the raw value.
 - the minimum and maximum should be printed out to the same number of decimals as the raw value
 - All percentages should be reported with one decimal point.
- All tables and figures will have a footnote indicating corresponding reference listing(s), such as “Reference Listing: xx.x”. Additionally, tables and figures will have a footnote indicating the corresponding reference table(s), if applicable.
- Footers should include data source, date of data extract/snapshot and SAS program name. If an additional cut-off date is being used; this should also be included. This should come after all relevant footnotes in the output.
- Tables will ensure page breaks don’t occur in the middle of statistical table blocks, unless unavoidable
- For listings with multiple records for subjects, repeat values of the subjects will be greyed out
- If a planned table does not have any data to summarize, it will still be created with the statement “No subjects qualify for this table.” This will also be applied to listings and figures.

11 TABLES AND LISTINGS SHELLS

This section will give the format and structure of all tables and listings to be produced. These detailed specifications can undergo minor revisions during the production phase without needing to revise the SAP. Minor revisions are defined as revisions that do not invalidate any of the specifications in this SAP.

Table 14.1.1 Subject Disposition – All Subjects

	Subjects
Patients Screened	xx
Populations, n (%)	
ITT ^a	xx (xx.x)
PP ^b	xx (xx.x)
Study Status, n (%)^c	
Subject completed the study	xx (xx.x)
Investigator withdrawal	xx (xx.x)
Subject withdrawal	xx (xx.x)
Subject died	xx (xx.x)
Other	xx (xx.x)

^a ITT is defined as subjects who were enrolled and meet the eligibility criteria.

^b PP is defined as ITT subjects without any major protocol deviation, such as missing SPECT-CT/SPECT scans.

^c Percentages are based on the number of subjects in the ITT population

Table 14.2.1 Primary Endpoint Summary – ITT Population

ITT Population (N=XX)	
Delivered Activity for Whole Body (MBq)	
Immediately following	
n	xx
Mean (SD)	xx (xx.x)
Median	xx
Q1, Q3	xx, xx
Min, Max	xx, xx
4 hours +/- 2 hours	
n	xx
Mean (SD)	xx (xx.x)
Median	xx
Q1, Q3	xx, xx
Min, Max	xx, xx
18-24 hours	
n	xx
Mean (SD)	xx (xx.x)
Median	xx
Q1, Q3	xx, xx
Min, Max	xx, xx
Delivered Activity for Non-Liver Critical Organs (MBq)	
Immediately following	
n	xx
Mean (SD)	xx (xx.x)
Median	xx
Q1, Q3	xx, xx
Min, Max	xx, xx
4 hours +/- 2 hours	
n	xx
Mean (SD)	xx (xx.x)
Median	xx
Q1, Q3	xx, xx
Min, Max	xx, xx
18-24 hours	
n	xx
Mean (SD)	xx (xx.x)
Median	xx
Q1, Q3	xx, xx
Min, Max	xx, xx
Absorbed Dose (Gy) – Whole Body	
n	xx
Mean (SD)	xx (xx.x)
Median	xx
Q1, Q3	xx, xx
Min, Max	xx, xx

ITT Population (N=XX)	
Absorbed Dose (Gy) – Non-Liver Critical Organs	
n	xx
Mean (SD)	xx (xx.x)
Median	xx
Q1, Q3	xx, xx
Min, Max	xx, xx
Effective Dose (mSv) – Whole body	
n	xx
Mean (SD)	xx (xx.x)
Median	xx
Q1, Q3	xx, xx
Min, Max	xx, xx
Effective Dose (mSv) – Non-Liver Critical Organs	
n	xx
Mean (SD)	xx (xx.x)
Median	xx
Q1, Q3	xx, xx
Min, Max	xx, xx

Programming note: delivered activity for non-liver critical organs is the sum of all the individual activity for non-liver critical organs including others. The same thing is applied to absorbed dose and effective dose.

Listing 16.2.1.1 Disposition – All Subjects

Subject ID	ITT Population	PP Population	Consent Date	Version of ICF	End of Study Date	End of Study Reason
xxxxxxxx	Yes	Yes	ddMMMyyyy	xx.xx	ddMMMyyyy	xxxxx
xxxxxxxx	No	No				Other: specify

Listing 16.2.1.2 Inclusion/Exclusion – All Subjects

Site #	Subject ID	Meet Eligibility?	Inclusion Criteria Not Met	Exclusion Criteria Met
xx	xxxxxxxx	Yes		
xx	xxxxxxxx	No	Inclusion 1: Patients 21 years and older; Inclusion 3: Patients who receive Tc-99m MAA while being evaluated for TheraSphere treatment	Exclusion 2: Patients who are contraindicated for Tc-99m MAA per the applicable Package Insert

Listing 16.2.1.3 Demographics – ITT population

Subject ID	Age at Consent (years)	Gender at birth	Race	Ethnicity	Height (unit)	Weight (unit)	BMI (kg/m ²) ^a	HCC Diagnosis Date for Current Treatment	Months since Diagnosis
XXXXXXXXXX	xx	xx	xx	xx	xx (cm)	xx (kg)	xx	ddMMMyyyy	xx.x
XXXXXXXXXX	xx	xx	xx	xx	xx (in)	xx (lb)	xx	ddMMMyyyy	xx.x

^aBMI is calculated as weight (kg)/height (m)²

Listing 16.2.1.4 Protocol Deviations – ITT population

Subject ID	Date of Deviation	Folder /Form	Category	Reason
xxxxxx	ddMMMyyyy		Other: specify	
xxxxxx	ddMMMyyyy		Event not reported per protocol: AE number	

Listing 16.2.2.1 Tc-99m MAA Administration – ITT population

Subject ID	Date of Administration	Time of Administration	Vascular Access	Tc-99m MAA activity in syringe before injection (unit)	Tc-99m MAA injection volume (cc)	Tc-99m MAA activity remaining in syringe (unit)	Location of Tc-99m MAA injection
xxxxxxx	ddMMMyyyy	xx:xx	Femoral Artery	xx (mBq)	xx	xx (mBq)	List all the locations
xxxxxxx	ddMMMyyyy	xx:xx	Radial Artery	xx (mBq)	xx	NA	
xxxxxxx	ddMMMyyyy	xx:xx	Femoral Artery	xx (mCi)	xx	xx (mCi)	

Listing 16.2.2.2 Imaging Information – ITT population

Subject ID	Time from Tc-99m MAA Administration	Image Modality	Date of Image	Time of Image
xxxxxxxx	Immediately following	SPECT-CT	ddMMMyyyy	xx:xx
	4 hours +/-2 hours	SPECT	ddMMMyyyy	xx:xx
	18-24 hours	SPECT	ddMMMyyyy	xx:xx
xxxxxxxx	Immediately following	SPECT-CT	ddMMMyyyy	xx:xx
	4 hours +/-2 hours	SPECT	ddMMMyyyy	xx:xx
	18-24 hours	SPECT	ddMMMyyyy	xx:xx

Listing 16.2.2.3 Tc-99m MAA Deposition – ITT population

Subject ID	Region	Volume (cc)	Activity (MBq)			Absorbed Dose (Gy)	Effective Dose (mSv)
			Immediately following	4 hours	+/- 2 hours		
XXXXXXXXXX	Liver	xx	xx		xx	xx	xx
	Lungs	xx	xx	xx		xx	xx
	Salivary gland	xx	xx	xx		xx	xx
	Thyroid gland	xx	xx	xx		xx	xx
	Stomach mucosa/wall	xx	xx	xx		xx	xx
	Gallbladder wall	xx	xx	xx		xx	xx
	Small intestine mucosa/wall	xx	xx	xx		xx	xx
	Colon mucosa/wall	xx	xx	xx		xx	xx
	Urinary bladder wall	xx	xx	xx		xx	xx
	Kidneys	xx	xx	xx		xx	xx
	Spleen	xx	xx	xx		xx	xx
	Heart wall	xx	xx	xx		xx	xx
	Other 1	xx	xx	xx		xx	xx
	Other 2	xx	xx	xx		xx	xx
	Other 3	xx	xx	xx		xx	xx
XXXXXXXXXX	Whole body	NA	xx	xx		xx	xx
	Liver	xx	xx	xx		xx	xx
	Lungs	xx	xx	xx		xx	xx
						
	Other 3	xx	xx	xx		xx	xx
	Whole body	NA	xx	xx		xx	xx

Programming note: For others, please population the actual region in specify field.

Listing 16.2.3.1 Procedure-Related Serious Adverse Events – ITT population

Subject ID	MedDRA SOC/ Preferred Term/ Verbatim Term	Onset Date	Awareness Date	Serious Criteria	Severity	Action Taken	Outcome
xxxxxx	System Organ Class/ Preferred Term/ VERBATIM TERM*	ddMMMyyyy	ddMMMyyyy	xx	xx	Other: specify	Resolved: Resolution date Death: Death date Surgery: specify Interventional procedure: specify

Programming note: For outcome, if it is Resolved or Death, please concatenate with date.

Boston Scientific

Project Document Signature Page

Report Generated: 29-Jul-2024 16:59:44 (GMT)

Criteria- Full Lifecycle (All Votes)

Object Number:	92813549	State:	Released
Name:	TheraSphere Statistical Analysis Plan	Revision:	B
Effective Date:	04-Jan-2023 06:21 GMT	Sub Type:	null
CN Number:	2573811		

Signatures:

Object Type	Number	Reviewer	Role	Vote	Vote Comments	Vote Date
Change Notice	2573811	[name]	Clinical Project Management - Functional Representative	Approve		04-Jan-2023 15:50 GMT
Change Notice	2573811	[name]	Medical - Functional Representative	Approve		04-Jan-2023 17:55 GMT
Change Notice	2573811	[name]	Biostatistics - Functional Representative	Approve		04-Jan-2023 18:21 GMT

92813549

1 of 1

Boston Scientific Confidential
Unauthorized use is prohibited

B

TheraSphere Statistical Analysis Plan

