6 ENDPOINT ANALYSIS

6.1 Primary Endpoint

The endpoints of the study are the mean absorbed doses and delivered activity for whole body and for non-liver critical organs (including whole body effective dose). Non-liver critical organs include lungs, salivary gland, thyroid gland, stomach mucosa/wall, gallbladder wall, small intestine mucosa/wall, colon mucosa/wall, urinary bladder wall, kidneys, spleen, and heart wall.

Tc-99m MAA activity is measured through SPECT-CT/SPECT scans immediately after the injection, 4 hours (within ± 2 hours window) after the injection, and between 18 and 24 hours after the injection. For each organ, a plot of activity and time from Tc-99m MAA administration will be constructed, and an appropriate graphing software will be used to fit a curve to the data. The cumulative activity (area under the curve) divided by the administered activity will be used as an input to S-value-based dosimetry software to determine absorbed dose and effective absorbed dose.

Descriptive statistics will be used to summarize delivered activity for whole body and for non-liver critical organs at post-Tc-99m MAA injection, 4 hours after the injection and 18-24 hours after the injection. Descriptive statistics will be also used to summarize the mean absorbed dose and effective dose for whole body and for non-liver critical organs.

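### The primary endpoint table adds absorbed dose (Gy) across organs, giving a figure that is not the dose to any organ, and no planned table reports a mean or SD for a single organ

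*SAP*

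**What the plan says.** The objective (Protocol section 6) is the absorbed dose of Tc-99m MAA to the whole body and to non-liver critical organs. Protocol 11.1 makes mean absorbed dose and delivered activity the endpoints, summarized by mean and SD.

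SAP 6.1 works organ by organ: "For each organ, a plot of activity and time from Tc-99m MAA administration will be constructed". The area under the fitted curve, divided by administered activity, then goes into the dosimetry software. The section names 11 organs ("Non-liver critical organs include lungs, salivary gland, thyroid gland, stomach mucosa/wall, gallbladder wall, small intestine mucosa/wall", then colon, urinary bladder wall, kidneys, spleen and heart wall). For the dose summary it says: "Descriptive statistics will be also used to summarize the mean absorbed dose and effective dose for whole body and for non-liver critical organs". It does not say whether organs are pooled, and it mentions no sum.

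The pooling rule appears only in the programming note to Table 14.2.1 in SAP section 11: "delivered activity for non-liver critical organs is the sum of all the individual activity for non-liver critical organs including others". The next sentence extends it: "The same thing is applied to absorbed dose and effective dose".

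Section 11 states that it covers all tables and listings. It has two tables, 14.1.1 (disposition) and 14.2.1 (primary endpoint). Organ-level values appear only patient by patient in Listing 16.2.2.3, which has the 11 named organs plus three rows for other regions, filled as free text: "For others, please population the actual region in specify field".

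**The concern.** The operation that the note carries over from activity to dose can only be the sum. That is sound for MBq, because the activity in two organs together is the total of the two. It is not sound for Gy. Absorbed dose is energy divided by the mass of one region, so the dose to two organs taken together is a mass-weighted mean of the two doses, not their total.

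Three consequences follow for the one table that reports the primary endpoint:

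- The Gy figure in the non-liver row is not the dose to any organ or to the combined tissue, and a reader could easily take it for one.
- The figure depends on how many regions are entered. Two patients with identical doses in the named organs get different values if one has an extra free-text region with any dose, so the mean and SD over five patients can mix sums with different numbers of terms.
- The table cannot show which organ received most. Protocol section 5 cites a 70-patient imaging series in which visible uptake ranged from all patients (renal cortex) through 46% (gastric mucosa) to 33% (salivary and thyroid glands). Those are frequencies of uptake, not doses, but they give reason to expect organs to differ.

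The SAP's validation step checks reports produced under the plan, so it cannot be relied on to catch an error in the plan itself.

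**Working it through.** The documents give no organ doses and no figure to reproduce. The check is a count of the planned outputs, followed by arithmetic that holds for any doses. Numerical doses below are assumed, for illustration only.

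**1. Blocks in Table 14.2.1.** Activity: 2 (whole body, non-liver organs) × 3 time points = 6. Absorbed dose: 2. Effective dose: 2. Total 10; blocks for a single organ: 0.

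**2. Number of terms in the sum.** SAP 6.1 names 11 organs and the Listing 16.2.2.3 shell shows three 'Other' rows. So k = 11 if every named organ has a value and no other region is entered, and k = 14 if all three 'Other' rows are also filled.

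**3. Bounds for any doses.** For organ doses dᵢ ≥ 0 and masses mᵢ:

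- Printed value: S = Σdᵢ = k × (unweighted mean of the dᵢ).
- True mean dose to the combined tissue: Σmᵢdᵢ / Σmᵢ.
- Ordering: Σmᵢdᵢ / Σmᵢ ≤ max(dᵢ) ≤ S ≤ k × max(dᵢ).

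The printed value is therefore never below the highest organ dose, and exceeds it as soon as a second organ has any dose. The true combined dose never exceeds the highest organ dose. The ratio S / max(dᵢ) lies between 1 and 11 for the named organs, and between 1 and 14 with three others.

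**4. Effect of the number of regions (assumed doses).** With every region at 1 mGy, the row shows 11, 12, 13 or 14 mGy for 0, 1, 2 or 3 other regions. No region received more than 1 mGy.

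**5. Spread of dose over organs (assumed).** Let 4 organs receive d and the other 7 receive f × d. The row prints (4 + 7f)d:

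| f | Printed value | Highest organ dose |
|---|---|---|
| 0 | 4.0d | d |
| 0.1 | 4.7d | d |
| 0.5 | 7.5d | d |
| 1 | 11d | d |

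**6. The sum hides the highest organ (assumed).** Eleven organs at 1 mGy give 11 mGy. Ten organs at 0.1 mGy and one at 10 mGy give 10 × 0.1 + 10 = 11 mGy. The printed value is the same, but the highest organ dose differs tenfold.

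**7. Sum against combined-tissue dose (assumed).** For 1.0 kg at 1 mGy and 0.02 kg at 5 mGy, the sum is 6 mGy and the mass-weighted dose is (1.0 × 1 + 0.02 × 5) / 1.02 = 1.08 mGy.

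**8. The SD (assumed).** If each of 11 organs has between-patient SD 1 and common correlation ρ, the SD of the sum is √(11 + 110ρ): 3.3 at ρ = 0, 8.1 at ρ = 0.5 and 11.0 at ρ = 1. The SD for an organ cannot be recovered from the printed SD.

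**The case against.** The strongest reply concerns severity. The study is descriptive, with five patients, no hypothesis test and no threshold that uses this row. Listing 16.2.2.3 prints dose for every organ and patient, and at this size the listing is the full organ data set. This stands in part: no data are lost and organ means can be worked out by hand. It does not make the printed Gy figure correct, and that figure sits in the only table for the only primary endpoint.

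Other points on that side:

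- *The shells may be incomplete.* SAP 7.1 promises a summary of demographics, and SAP 6.1 plans activity–time plots; section 11 has no table for the first and no figure shell for the second. An organ-level summary might still be intended. But section 11 claims to cover all tables, and the note says how the dose row is filled.
- *Protocol 11.1 is ambiguous.* Its call for a mean and SD for each endpoint may mean whole body and organs as two groups. That is a fair reading, but even then a sum of doses is not a mean absorbed dose.
- *The factors 11 and 14 are conditional.* They assume a value for every region, and nothing caps the other regions at three. This is correct, and the bounds should be read that way.
- *Activity is pooled too.* It is, but total MBq is a meaningful quantity. Activity by organ would be a useful addition (11 × 3 = 33 further blocks); it does not correct an error.
- *Effective dose may legitimately be summed.* It may, if each organ entry is already a tissue-weighted contribution. The SAP does not say.

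**Conclusion.** The concern holds and should be corrected before analysis. Under the stated rule, the non-liver absorbed-dose row of Table 14.2.1 will not be the dose to any organ or tissue. It will be at least the highest organ dose and, with all 11 named organs entered, up to 11 times that dose (14 times with three other regions). These bounds need only non-negative doses and that number of terms. Where the true ratio falls cannot be said, because the documents give no organ doses.

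Separately, no planned table gives a mean or SD for any single organ. The harm is limited to the summary, since the listing preserves the organ-level values. The criticism of the effective-dose row is conditional on what the listed organ entries represent.

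**What to change.** Amend the SAP before analysis:

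1. Replace the single non-liver absorbed-dose row in Table 14.2.1 with one block for each of the 11 named organs (n, mean, SD, median, quartiles, minimum, maximum), and show any other region by name.
2. Limit the summation note to delivered activity. Suggested wording: *Absorbed dose is summarized separately for each organ and is not summed.*
3. State whether the effective-dose entries by organ are tissue-weighted contributions. If so, keep the sum and label it a partial contribution to whole-body effective dose. If not, drop the row.

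An amendment is the safer route. The SAP lets shells change without revision only within limits, "Minor revisions are defined as revisions that do not invalidate any of the specifications in this SAP", and removing the Gy sum reverses a stated rule. SAP section 8 provides that changes made before the analysis "will be documented in an amended SAP approved prior to performing the analyses". If the analysis has already been run, section 8 requires the change and its reason in the clinical study report.

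The cost is the amendment and a longer table: 10 − 1 + 11 = 20 blocks, plus one for each other region shown. The values are already planned for Listing 16.2.2.3, so no new data or patients are needed. With five patients, SDs and quartiles for each organ will be imprecise.
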